9.3.4 Covariates

The covariates of interest are age, gender, body mass index (BMI), blood pressure, blood glucose level, and HbA1c, if available. Comorbidities of interest include hypertension, dyslipidaemia, kidney diseases, kidney stones, history of kidney transplant, liver diseases, prostate diseases, pancreatitis, surgery, infections (other than UTIs) and heart diseases, if available. In addition, genital defects, urinary tract anatomical defects, lab variables (CBC, FPG, OGTT, ketones level, amylase, lipase, arterial blood gas, pH, bicarbonate, ScCr, lipid profile tests, BUN, liver tests, INR and platelets) and concomitant medications [REDACTED] will be considered as covariates. All these covariates will be identified, if available, for all cohort members prior to and including the index date. Severity of T2DM will be assessed by HbA1c values, concomitant diagnoses and duration since the first diagnosis, when available.

These and other variables that can differ by exposure group will be considered for inclusion as predictors in the logistic regression models used to generate the propensity scores.

Propensity scores will be used in the analysis to quantify the probability of receiving Empagliflozin at the index date for new users of both Empagliflozin and DPP-4 inhibitors.

At the index date, cohort members will also be classified by indicator variables on the calendar time of cohort entry (by quarter) whether the index treatment (Empagliflozin or DPP-4 inhibitor) was added to existing medication (adding on), or if the index treatment was initiated as a replacement for another GLD (switching from the existing GLD to Empagliflozin or DPP-4 inhibitor), and whether this treatment was received as monotherapy or as dual or triple therapy. A variable indicating whether or not patients were receiving insulin at the index date will also be created.

List of Variables, (other variables will be added during the study period)

Demographics

1. Age
2. Gender

Hospitalization, when available

3. Admission date
4. Place admitted from
5. Outcomes diagnosis date
6. Place of diagnosis (ER, Inpatients, Outpatient)

Treatment

7. Treatment initiation date
8. Treatment discontinuation date

Outcomes, when available

9. Date of DKA diagnosis
10. Date of UTI diagnosis
11. Date of dehydration diagnosis
12. Date of volume depletion diagnosis
13. Date of death
14. Primary cause of death
15. Date of discharge
16. Date of admission
17. Reason for admission

Lab variables / Vital signs, when available

18. Weight
19. Height
20. CBC
21. Blood glucose
22. HbA1c
23. FPG
24. OGTT
25. Ketones (Urine and/or blood)
26. Blood pressure
27. Amylase
28. Lipase
29. Triglyceride (TG)
30. Liver function tests
31. Arterial blood gas
32. pH
33. Bicarbonate
34. Lipid profile tests
35. INR
36. eGFR
37. CrCl
38. ScCr
39. BUN

Comorbidities, Medical History

40. Diabetes
41. Kidney diseases
42. Hypertension
43. Heart failure
44. Acute coronary diseases
45. Heart diseases
46. Diabetic ketoacidosis

47. Pregnancy
48. Abdominal trauma
49. Kidney stones
50. Body paralysis (paraplegia or quadriplegia)
51. Pancreatitis
52. Dyslipidaemia
53. Cerebrovascular disease
54. Pulmonary disease
55. Hypothyroidism
56. Hyperthyroidism
57. Surgery
58. Liver disease
59. HIV/AIDS
60. Cancer
61. Hepatitis “A,B,C”
62. Cholestatic hepatitis
63. Acute liver disease
64. Liver cirrhosis
65. Kidney transplant
66. Prostate diseases
67. Burns
68. Genital defects
69. Urinary tract anatomical defects
70. Other liver diseases

Prior medications exposure in the last 6 months and during the study period

71. Empagliflozin
72. Sitagliptin
73. Saxagliptin
74. Vildagliptin
75. Alogliptin
76. Linagliptin
77. Insulin (all types)
78. Metformin (single or combination)
79. Sulfonylureas
80. Meglitinides
81. Thiazolidinediones
82. α -glucosidase inhibitors
83. Glucagon-like peptide-1 receptor agonist
84. Lipid lowering agents (Statins, Fibrates, Niacin)
85. Antihypertensive agents (Diuretics, ACEIs, B-blocker)
86. Antipsychotic medications
87. Corticosteroids

9.4 DATA SOURCES

This study will be carried out in the manner of successive survey that the investigator will be asked to successively write in the case report forms (e-CRFs) from the subject who was initially administered the drug following the study start date to the requested number of subjects without omission. Prior to initiation of the study, a written contract shall be concluded, with the head of the site or the investigator with his/her consent for non-interventional study with new data collection.

This study will be carried out in the manner of successive surveys where the investigator will be asked to write in the case report forms (e -CRFs). Number of recruited patients will be comparable in each group within a given timeframe (i.e each site will ensure to recruit similar number of patients for each group according to assigned blocks of enrolment). Data on the period preceding the index date will be collected at the time of the first survey.

The site(s) will be primary care clinics, hospital clinics and other outpatient clinics. Data from hospitals will be documented when needed, especially if there are cases of admission for one of the study outcomes. Discharge data will always be documented by the investigator when needed.

Demographics (age, gender), comorbidities (cardiac, hepatic, oncologic, renal, neurologic, immunologic, respiratory and vascular), previous and current hypoglycaemic agent exposures (biguanides, sulfonylureas, meglitinides, thiazolidinediones, dipeptidyl peptidase-4 inhibitors, α -glucosidase inhibitors, glucagon-like peptide-1 receptor agonists and insulin), and laboratory data (complete blood count, blood glucose level “all available types”, and HbA1c) variables will be obtained from either the medical record or during the first survey (Section 9.3.4).

9.5 STUDY SIZE

The sample size is of 1500 patients; it is based on SFDA requirements. As per SFDA regulation and requirements to detect the DKA cases, 750 patients will be enrolled in each group (DPP4i and SGLT-2i). The number of recruited patients will be comparable in each group within a given time frame (i.e. each site will ensure to recruit similar number of patients for each group according to assigned blocks of enrolment). In addition, prevalence of the primary outcomes was searched in literature and a study found assuming the prevalence to be around 25% (urinary tract infection and other risk factors) among Saudi patients with diabetes.

9.6 DATA MANAGEMENT

Patients’ data will be gathered by e-CRF. The data management procedures to ensure the quality of the data are described in detail in the data management plan (DMP) available in TMF. Data management and statistics will be outsourced to a qualified contract research organization (CRO).

9.7 DATA ANALYSIS

Details of all analyses and variables specification will be defined in a separate SEAP.

Patients are grouped according the exposure to either Empagliflozin or DPP-4 inhibitors. Data will be analysed per group. Let the index period define the time from index date to the end of treatment as defined in [section 9.3.2](#) by current use, and the follow-up period the time from index date to the end of observation as defined in [section 9](#). Incidences will be derived if events of interest occur in the respective period. The main analysis will consider index periods only, a secondary analysis will consider only the time of the index period in the month of Ramadan in every year, while sensitivity analyses will consider respective follow-up periods, overall or during Ramadan only. Times from index date to first occurrence will also be determined per event of interest and described by means of Kaplan-Meier estimates and median times with 95% confidence intervals, where appropriate.

All individual data will be listed and described per group by means of summary tables presenting frequency counts and percentages for categorical data and arithmetic means, standard deviations, medians, minimum and maximum values for continuous data. Baseline is defined as the last observation on or before the index date.

For the assessment of the primary and secondary objectives, the main data analysis will be conducted in two stages:

- 1) Construction of the PS by modelling the exposure to Empagliflozin vs. DPP-4 inhibitor;
- 2) Estimation of the effect of exposure to Empagliflozin on the risk of ketoacidosis, severe urinary tract infections, volume depletion and dehydration compared to those exposed to DPP-4 inhibitor.

Propensity score stratification will be the primary method to control for the confounders in the analysis phase. The stratification will divide the study population in several groups (max. 5 groups) based on their propensity score value. Propensity score matching will also be used as secondary method in the analysis phase.

All statistical tests will be conducted with a two-sided significance level alpha of 0.05 and all analyses will be conducted using SAS statistical analysis software version 9.4 (SAS Institute, Inc., Cary, NC) or later.

9.7.1 Propensity score modelling

A propensity score (PS) method will be utilized to control for confounding in the analysis phase. It is used to balance the baseline covariates predictive of treatment, to lessen the unequal chance of receiving Empagliflozin versus DPP-4 inhibitors. PS will be estimated with logistic regression for each cohort member. PS is one of effective methods used in epidemiological studies analyses.

Bivariate analysis will be initially used for the selection of potential clinical covariates for inclusion in the propensity score model. Demographic and clinical categorical data will be analysed using an χ^2 or Fisher's exact test while continuous variables will be analysed using a student's t-test or Mann-Whitney U test.

The model will be selected in a process optimizing the goodness of fit. Only clinically relevant, statistically significant (p-value <0.25) covariates will be included. Propensity

[figure not shown]
scores will be stratified into quintiles, and subsequent covariate balance will be reviewed graphically and with Mantel-Haenszel tests.

9.7.2 Main analysis using stratification

For the incident users of Empagliflozin along with their respective comparators, analysis will be performed using the “as-treated” (AT) approach. This corresponds to censoring individuals who discontinue use of the index drug, i.e. who either switch from the index drug to any other of the index drugs (Empagliflozin or DPP-4 inhibitor) during follow-up or who stop using the index drug. The AT approach is considering index periods.

For each event of interest, ketoacidosis, severe urinary tract infections, volume depletion, and dehydration, crude and adjusted incidence rates per cohort will be described and compared by means of incidence rate ratios (IRR). Incidence rates will be reported as point estimates and 95% confidence intervals (CIs). Crude incidence rates will be adjusted per 1,000 person-years. Per cohort and, where appropriate per stratum and/or subgroup, the number of person-years is the sum of length of index periods of all patients. Time to first event occurrence will be compared by means of hazard ratios and their 95% confidence intervals.

IRRs and hazard ratios are analysed using stratification. Strata are defined by PS quintiles. IRRs are investigated by means of a stratified Mantel-Haenszel analysis, while hazard ratios are investigated by means of a Cox regression, if proportional hazards can be assumed.

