9. RESEARCH METHODS

This is a non-interventional study with new data collection.

This study will cover the period between Q3 2018 and Q4 2020. The main goals of this study are to examine the risk of ketoacidosis, severe urinary tract infections, volume depletion, and dehydration associated with the use of Empagliflozin compared to the use of DPP-4 inhibitors in T2DM patients. The study will use an “incident users” design and compare new users of Empagliflozin with new users of DPP-4 inhibitors. The index date will be defined as the date on which each identified new user receives the index prescription for Empagliflozin or DPP-4 inhibitors. The definition of drug exposure for Empagliflozin will be any patient using at least one prescription of Empagliflozin tablets (10 or 25 mg) or fixed-dose combinations with metformin. The comparator group will be comprised of patients with at least one prescription of a DPP-4 inhibitor: sitagliptin, saxagliptin, linagliptin, vildagliptin, alogliptin (and fixed-dose combinations of these drugs with metformin). Each member of the population exposed to Empagliflozin must have at least one prescription for Empagliflozin, with or without other Glucose-lowering Drugs (GLDs,) and no prior prescriptions of a DPP-4 inhibitor or Empagliflozin during the available pre-index period. Each member of the population exposed to a DPP-4 inhibitor must have at least one prescription for a DPP-4 inhibitor, with or without other GLDs, and no prior prescriptions of a DPP-4 inhibitor or Empagliflozin during the available pre-index period.

Follow-up will start the day after the index date and will continue until any of the following conditions are met: date of death or after 12 months of follow-up, or the date during follow-up that specific exclusion criteria are met, the date of the last continuous treatment of the index drug (Empagliflozin or DPP-4 inhibitor) plus a defined grace period (30 days after the end of the last prescription’s days’ supply in main analyses), or the date in which a new treatment episode starts with any of the other index drugs. Patients who discontinue an index drug and then subsequently initiate another index drug will not be allowed to re-enter the study. Patients will be followed-up for 12 months.

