9.2.2.5 Follow-up period

Follow-up will start the day after the index date and last until end of study data (date of death or date of study end), the date during follow-up when specific exclusion criteria are met, the end date of the treatment of the index drug (Empagliflozin or other SGLT2 inhibitor or DPP-4 inhibitor) plus a defined grace period (30 days after the end of the last prescription's supply in main analyses), or the date on which a new treatment episode starts with any of the other index drugs.

Patients with adverse events noted at the final follow-up visit or upon premature discontinuation of Empagliflozin or the comparator DPP-4 inhibitor will be monitored further until the resolution of those adverse events. Alternatively, those patients will be followed up until the PASS physician and sponsor agree that no further follow-up is necessary.

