9.3.2 Exposures

The definition of drug exposure for Empagliflozin will be any patient using at least one prescription of Empagliflozin tablets (10 or 25 mg) or fixed-dose combinations with metformin. For the comparator group, the patients will have at least one prescription of DPP-4 inhibitors. DPP-4 inhibitor users included in this study will be using one of the following approved drugs in Saudi Arabia: Sitagliptin, Saxagliptin, Vildagliptin, Alogliptin, Linagliptin, or fixed-dose combinations of these drugs with metformin. [R17-3427]

Furthermore, each member of the population exposed to Empagliflozin must have at least one prescription for Empagliflozin, with or without other glucose-lowering drugs (GLDs), and have no prior prescriptions of a DPP-4 inhibitor or Empagliflozin during the available pre-index period. Each member of the population exposed to a DPP-4 inhibitor must have at least one prescription for a DPP-4 inhibitor, with or without other GLDs, and no prior prescriptions of a DPP-4 inhibitor or Empagliflozin during the available pre-index period.

Add-on therapy will be allowed after using the exposure of interest as the initial drug for new users. Therefore, using the drug as part of dual therapy or triple therapy will be allowed.

The use of studied medications will be defined on different levels: current use, recent use and discontinuation of the studied drugs. Current use of the index drugs will be defined from the date of prescription of Empagliflozin or DPP-4 inhibitor to the end of supply for that prescription plus a period of 30 days. Recent use will be defined from the end of current use (30 days after end of supply) until 90 days later (which is 120 days after end of supply).

Discontinuation of the index drug will be defined as no further prescription 120 or more days after the end of the last prescription's supply. Patients who discontinue an index drug and then subsequently initiate another index drug will not be allowed to re-enter the study.

Patients switching to or adding Empagliflozin to other antidiabetic medications will be compared to patients switching to or adding comparator treatment on the same background therapy. Identification of a "new-user" design is an appropriate method for studying second-line therapies in chronic conditions.

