3 STUDY OVERVIEW

The study will use an “incident users” design and compare new users of EMPAGLIFLOZIN with new users of DPP-4 inhibitors.

This study will be carried out by conducting successive surveys over the follow-up period. The investigator will be asked to record the information from the surveys in the case report forms

Statistical Analysis Plan (SAP)

Document Date: 17APR2019

Document Version: 1.0 Final

(e-CRFs) from each subject who was initially administered the drug following the study start date until the requested number of subjects is reached.

The index date for each identified new user is defined as the date on which they receive the index prescription for EMPAGLIFLOZIN or DPP-4 inhibitors.

Patients are enrolled if at least 18 years of age at the index date, diagnosed with T2DM in Saudi Arabia, and who have not used other SGLT2 inhibitors during the previous 12 months. Patients are not enrolled if they have known hypersensitivity to EMPAGLIFLOZIN, the comparator DPP-4 inhibitors or any of their excipients, if EMPAGLIFLOZIN or the comparator DPP-4 inhibitor is contraindicated according SFDA approved label, or if they are on prescribed fixed-dose combinations of SGLT2 inhibitors with DPP-4 inhibitors.

Follow-up will start the day after the index date and will continue until any of the following conditions are met:

- Death
- 12 months of follow-up
- specific exclusion criteria are met during follow-up
- the last continuous treatment of the index drug (EMPAGLIFLOZIN or DPP-4 inhibitor) plus a defined grace period (30 days after the end of the last prescription's days' supply in main analyses)
- a new treatment episode starts with any of the other index drugs.

Patients who discontinue an index drug and then subsequently initiate another index drug will not be allowed to re-enter the study.

Four study visits will be held, at baseline, after 16, 32 and 52 weeks of follow-up.

[figure not shown]
[REDACTED]

Statistical Analysis Plan (SAP)

Document Date: 17APR2019

Document Version: 1.0 Final

Figure 3-1: Study Visits

* from Visit 1

Table 3-1: Schedule of Visits

Assessment	Visit 1	Visit 2	Visit 3	Visit 4
Informed Consent	X			
Demographics	X			
Diagnosis	X			
Medical History	X			
HbA1c	X	*	*	*
Blood glucose level	*			
Other Laboratory/Renal Function	*			
Physical Examination (for vital signs)	X	*	*	*
Concomitant Medication incl. anti-hyperglycemic	X	#	#	#
Dose of Empagliflozin / DPP-4 inhibitor	X	#	#	#
Adverse Events		X	X	X

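### The documents disagree on which drugs end person-time, and the main-analysis index period has no stop when a DPP-4 inhibitor patient adds a non-index SGLT2 inhibitor

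*Protocol*

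**What the plan says.** **Switching and stopping.** Under the as-treated approach, Protocol 9.7.2 censors patients who move during follow-up from the index drug to "any other of the index drugs (Empagliflozin or DPP-4 inhibitor"), and those who stop the index drug.

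**Follow-up.** Protocol 9 ends follow-up at "the date of the last continuous treatment of the index drug (Empagliflozin or DPP-4 inhibitor) plus a defined grace period", or at "the date in which a new treatment episode starts with any of the other index drugs". SAP 3 repeats this: one of its stops is that "a new treatment episode starts with any of the other index drugs", and it too names the index drugs as empagliflozin or a DPP-4 inhibitor. Protocol 9.2.2.5 uses a wider list: "the end date of the treatment of the index drug (Empagliflozin or other SGLT2 inhibitor or DPP-4 inhibitor) plus a defined grace period". All three places also end follow-up when certain exclusion criteria are met, without saying which ones.

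**Index period.** Protocol 9.7 bases the main analysis on index periods only and defines them through current use in 9.3.2, which runs from prescription to the end of supply plus 30 days. SAP 4.4 ends the index period at the end of treatment with empagliflozin or the DPP-4 inhibitor.

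**Add-on drugs.** Protocol 9.3.2: "Add-on therapy will be allowed after using the exposure of interest as the initial drug for new users". No exception is made for other SGLT2 inhibitors.

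**The concern.** At entry the plan treats SGLT2 inhibitors as a class: Protocol 9.2.2 and SAP 3 and 4.5 bar recent users. After entry, the rule for the main analysis names empagliflozin alone from that class. A comparator patient who keeps the DPP-4 inhibitor and adds a different SGLT2 inhibitor has neither switched to a named index drug nor stopped one, so the time and events after the addition stay in the comparator arm.

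The study exists to detect excess risk on empagliflozin. If the added drug carries a similar risk, the comparator rate rises and the IRR shrinks, which is the unwelcome direction in a safety study. The Ramadan analysis inherits the gap, because SAP 4.4 defines its period as a part of the index period. Two programmers could also apply different stops, depending on whether they worked from Protocol 9 or from 9.2.2.5.

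**Working it through.** No figure in the plan bears on this point. The 1,500 patients (750 per group) are set by the regulator, with no effect size or event rate, so there is nothing to reproduce. The check has two parts.

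**1. Which text governs a DPP-4 inhibitor patient who adds another SGLT2 inhibitor and continues the DPP-4 inhibitor?**

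| Place | Period governed | Does the addition end it? |
|---|---|---|
| Protocol 9.7.2 | Index period (main analysis) | No: not a named index drug, and the index drug is not stopped |
| Protocol 9.3.2 and 9.7 | Index period | No: supply of the DPP-4 inhibitor continues |
| SAP 4.4 | Index period | No: treatment continues |
| Protocol 9, SAP 3 | Follow-up | No under the new-episode stop; unknown under the exclusion-criteria stop |
| Protocol 9.2.2.5 | Follow-up | Yes, if its wider list also applies to its new-episode stop |

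The only text that would end this patient's time governs follow-up. Protocol 9.7 also takes the follow-up period from section 9, not from 9.2.2.5.

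**2. How much could it matter?** Let R be the true IRR of empagliflozin against DPP-4 inhibitor, f the share of comparator person-time with an added SGLT2 inhibitor, and Rs the rate ratio in that share. The comparator rate is multiplied by (1 − f) + f × Rs, so

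observed IRR = R / [(1 − f) + f × Rs].

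R, f and Rs are all assumptions; the documents give none of them. With a shared effect (Rs = R):

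| True IRR | f = 1% | f = 5% | f = 10% |
|---|---|---|---|
| 2 | 2/1.01 = 1.98 | 2/1.05 = 1.90 | 2/1.10 = 1.82 |
| 3 | 3/1.02 = 2.94 | 3/1.10 = 2.73 | 3/1.20 = 2.50 |

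To put f in terms of patients: if a share a of comparator patients adds such a drug evenly over the year and stays on it, f is about a/2. Shares of 2%, 5% and 10% give f of 1%, 2.5% and 5%, and a true IRR of 2 becomes 1.98, 1.95 and 1.90. Reaching f = 10% would take about 20% of the comparator arm, or 150 of 750 patients.

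For comparison, 20 against 10 events over equal person-time gives an IRR of 2 with standard error of the log √(1/20 + 1/10) = 0.387 and a 95% CI of about 0.94 to 4.27.

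If the added drug has a different effect, the shift need not be toward 1: R = 1, Rs = 2, f = 10% gives 1/1.10 = 0.91.

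**The case against.** - **Other text stops this patient.** A reader might infer that no passage covers the case. That is too strong. Protocol 9.2.2.5 can be read as ending follow-up here, and so might the exclusion-criteria stop. Both govern follow-up, however, and the main analysis uses the index period. The exclusion criteria are not listed either. The one in SAP 4.5 on SGLT2 inhibitor use looks back from entry; applied literally after the index date, it would remove every empagliflozin patient. The fixed-dose combination criterion does not reach separate tablets. This objection changes the finding into a conflict between passages but does not close the gap.
- **The empagliflozin arm.** A reader might also infer from 9.2.2.5 that a patient who moves from empagliflozin to another SGLT2 inhibitor stays in the empagliflozin arm. The main analysis does not allow it: that patient has stopped the index drug and is censored under 9.7.2.
- **The bias is not demonstrated.** This stands. It needs patients who add such a drug while staying on the DPP-4 inhibitor, and a similar effect of that drug. The documents lend some support to a shared effect: Protocol 7 links urinary tract infection to SGLT2 inhibitors generally, and 9.3.3 speaks of ketoacidosis induced by the class. They do not quantify it.
- **The shift is small beside sampling error.** Also true at low f. But wide intervals do not excuse placing events in the wrong arm, and Protocol 9.9 accepts that numbers may be low for ketoacidosis. With equal person-time, 4 against 1 events is an IRR of 4; one further case in contaminated comparator time makes it 4 against 2, an IRR of 2.
- **Sensitivity analyses may cover it.** The protocol abstract promises analyses with alternative exposure definitions, and parts of both documents are withheld from view, so this cannot be judged. A sensitivity analysis would not settle the main rule in any case.

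**Conclusion.** The finding is an inconsistency with a consequence for the main analysis. The documents disagree on which drugs end person-time, and the index-period rules as written leave SGLT2-exposed time in the comparator when a patient adds a non-index SGLT2 inhibitor and continues the DPP-4 inhibitor.

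The attenuation is conditional on a shared effect and on an add-on rate that the documents do not give. Over assumed shares of 1% to 10% of comparator person-time, the IRR falls by about 1% to 9% when the truth is 2, and by about 2% to 17% when it is 3. The documents do not support calling this a demonstrated or certain bias toward 1. It is worth correcting because the remedy is cheap and the likely direction is toward hiding risk.

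**What to change.** Reconcile Protocol 9, 9.2.2.5 and 9.7.2 with SAP 3 and 4.4 into a single analysis rule:

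- In either cohort, censor index-period and follow-up person-time at the first start of any non-index SGLT2 inhibitor (including fixed-dose combinations) or of the other index class, whether added or substituted.
- Use one index-drug list throughout both documents.
- State which exclusion criteria end follow-up after the index date.
- Derive the start date from the anti-hyperglycaemic changes already recorded at Visits 2 to 4. The variable list in Protocol 9.3.4 names no SGLT2 inhibitor besides empagliflozin, but it is declared open and the visit records cover any new agent, so the SAP need only specify the derivation.

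This concerns how time is counted in the analysis, not what patients may be prescribed. The cost is wording in two documents, one derived date and a small loss of person-time.
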